# THE HOUSTON HOME-BASED INTEGRATED INTERVENTION TARGETING BETTER ASTHMA CONTROL (HIITBAC) FOR AFRICAN AMERICANS

#### Statistical Analysis Plan

### Revision Dated 9/9/2018

## Power and Sample Size

Power and sample size calculations were performed using the PS program of Dupont and Plummer. The study was initially designed to recruit 300 patients in total. Based on the literature and our previous experience with the targeted participant population, we estimated a 35% LTF rate, resulting in 97 patients per group at the end of the study.

The primary outcome measures were the ACT™ score, MiniAQLQ score, and self-reported ED visits. For the ACT™ score, assuming a standard deviation of 4, a sample size of 97 participants per group gave greater than 99% power to detect a minimal clinically important difference (MCID)—which has been determined to be 3 for the ACT™ score—at the significance level of 0.05 (2-sided) using an independent, two-sample t-test assuming equal variances. For the MiniAQLQ score, assuming a standard deviation of 0.6, a sample size of 97 participants per group provided roughly 99% power to detect a MCID—which has been determined to be 0.5 for the MiniAQLQ score—at a significance level of 0.05 (2-sided) using an independent, two-sample t-test assuming equal variances. For ED visits, assuming a standard deviation of 3 for the number of self-reported ED visits for asthma over the previous 12 months, a sample size of 97 per group provided about 90% power to detect a difference of 1.4 in annual ED visits between the two groups at the significance level of 0.05 (2-sided) using an independent, two-sample t-test assuming equal variances.

### Randomization

We used a permutated block design with varying block sizes, stratified by age (less than 55 and 55 years or older) and sex, to randomize enrollees into either the clinic-only or home-visit group. The randomization program was written into our online HIITBAC CTMS. Randomization was done at the end of the baseline clinic visit. No one knew the randomization status until the baseline visit was completed. Subsequently, the clinical and home-visit teams were aware of the randomization status, which was needed to provide customized standard of care. The persons

making the mid-year phone calls were blinded to randomization status. No data analysis aside from data audits, validity checks and summary data for the Data Safety Monitoring Board was begun until the intervention and data collection were completed.

#### Statistical Analysis

Summary statistics were calculated for the entire cohort, stratified by treatment group. Baseline demographics, clinical outcomes, and environmental exposures were summarized by means (standard deviations), medians (ranges), or frequencies (percentages). Baseline characteristics were compared between treatment groups using an independent two-sample t-test, Wilcoxon rank sum tests, chi-square tests, or Fisher's exact test. Baseline summary statistics were also compared between patients who completed the study (N=193) and those who did not (N=71). All hypothesis tests were two-sided and assessed at the 0.05 level of significance.

Primary Outcome Analyses. The primary outcome measures of interest for this study were the ACT™, MiniAQLQ, and ED visits in the previous 12 months at exit. The ACT™ score is the sum of the scores of the 5 items included in the questionnaire. If any of the five items was missing a response, then no score was computed. The MiniAQLQ scores were computed using two methods, per scoring recommendations. The MiniAQLQ was first computed as the average of the scores for the 15 items. If any of the 15 items was missing a response, then no score was calculated. Alternatively, the MiniAQLQ was also scored if 2 or fewer responses were missing by replacing the missing responses with the worst score (regression to the null). After replacement, the MiniAQLQ was then calculated as the average of the scores for the 15 items. The alternative MiniAQLQ was used as the primary measure for asthma quality of life. ED utilization was measured by the frequency of visits to an ED during the 12-month period prior to the exit visit.

The initial analysis of the outcome measures used an independent, two-sample, two-sided t-test, assuming equal variances, to compare the mean ACT™ scores, MiniAQLQ scores, and ED visits over the previous 12 months between treatment groups at study exit. The equal variance assumption was tested using the F test at the .05 level and, if rejected, Welch's t-test approximation was used as alternative analysis. Approximate normality was assessed by using histograms, box-plots, skewness, kurtosis, and the Shapiro-Wilks test. Departures from

normality were addressed by using nonparametric analytic methods or data transformation.

In addition to the t-test, the Wilcoxon rank-sum test and Fisher's exact test were used to compare treatment groups for the ED visits outcome measure. The Wilcoxon rank-sum test was used to test for significant differences in the location of the distribution of ED visits between treatment groups. The outcome measure was also redefined as a binary outcome to compare the proportion of participants who had at least one visit to the ED by treatment group using the Fisher's exact test. Other outcome measures were similarly compared between treatment groups using t-tests, Wilcoxon rank-sum tests, chi-square tests, or Fisher's exact tests.

To assess between-group differences for the primary outcome measures, we calculated the raw mean difference (MD) for the continuous variables, ACT™ and MiniAQLQ; and the odds ratio (OR) for the binary variable, ED visits.

Exploratory Analyses. Data on ACT™, MiniAQLQ and ED visits were collected at baseline, and approximately 6 months and 12 months after enrollment. As an initial exploratory analyses of our primary outcome measures, we performed a repeated measures analysis using a general linear mixed model (LMM) for the continuous variables (ACT™ and MiniAQLQ) and a logistic regression using a generalized estimating equation (GEE) for categorical data (ED visits) to examine change over time. These models assume an intent-to-treat analysis. The LMM and GEE models include all available observations in the analyses and assume the data are missing at random, applying the restricted maximum likelihood estimation method. For the repeated measures analyses, we included time, study group, and the interaction between time and study group. The slopes between baseline and 6 months and 6 months and exit were calculated for each treatment group. The difference between treatment groups was compared at each time point. For the ACT™ and MiniAQLQ scores, the LMM was used to compute the difference in means and 95% confidence intervals (Cls) for effect size between the two treatment groups between baseline and exit. The logistic regression model was used to estimate the odds of having at least one ED visit in the 12-month period before exit compared with the 12-month period before baseline. The model was used to compute the odds ratio (OR) and 95% CIs for the effect size between the two treatment groups between baseline and exit.

We also performed exploratory analyses of potential predictor variables. Independent

linear regression models were used to explore the association between various demographic, clinical and housing baseline characteristics and the primary continuous outcome measures, ACT™ and MiniAQLQ, adjusting for study group and baseline scores. Predictor variables were selected for inclusion in the final multivariable linear regressions based on statistical significance (generally alpha = .05), frequency of missing observations, clinical relevance, and model fit statistics such as the R-squared value. Residual plots and diagnostics were used to assess linear regression model assumptions. Independent logistic regression was similarly used to assess the association between baseline demographic, clinical and housing characteristics and exit ED visits (yes/no), adjusting for study group and baseline ED visits. A multivariable logistic regression model was similarly constructed for key predictor variables of ED visits at exit.

In addition, we performed a number of post hoc subgroup analyses including (1) enrollees who completed all five home visits; (2) enrollees who did not change addresses during the intervention; and (3) enrollees who exited before Hurricane Harvey. We also examined the heterogeneity of treatment effect (HTE) by looking at the interactions between age and treatment group, and gender and treatment group. Interaction terms were assessed in linear regression models. All HTE analyses were post hoc and exploratory in nature.

Analyses were done using SAS 9.4 (Cary, NC) and Stata 15 (College Station, TX).

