For healthcare utilization outcomes (e.g., ED visits), assuming a standard deviation of 3 for the number of ED visits for asthma per person per year and nearly 90% power, a sample size of 97 per arm will allow us to detect a difference of 1.4 in annual number of ED visits between the two groups at the significance level of 0.05 (2-sided).

For this protocol, we are requesting approval of a sample size of 5,000. This includes approximately 4,000 possible screen/fails. This will also allow us to enroll slightly more than 300 without submitting an amendment to the IRB. The primary reason for enrolling more than 300 would be an unexpectedly high drop-out rate.

Provide a description of your plan for data analysis. State the types of comparisons you plan (e.g. comparison of means, comparison of proportions, regressions, analysis of variance). Which is the PRIMARY comparison/analysis? How will the analyses proposed relate to the primary purposes of your study?

All analyses will be performed according to treatment assignment, and all available data will be included in the evaluations, regardless of whether or not the subjects discontinue the assigned treatment (modified intention-to-treat analysis). Bivariate associations will be examined using Student t-tests and chi-square tests, as appropriate. Linear and logistic regression models with generalized estimating equation variance estimates will be used to evaluate differences among treatment groups for continuous or dichotomous outcomes, respectively. Unadjusted analysis will be performed as the primary results. If baseline covariate imbalance is detected, the analysis will adjust for imbalanced covariates. Subgroup analyses will be performed in pre-specified groups defined by age, sex, race, and asthma severity. P values of less than 0.05 (2-sided) will be considered statistically significant. P values will not be adjusted for multiple comparisons. Analyses will be carried out using the current versions of SAS, Stata, or R.

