We will collect blood samples, which may be stored for a long time or indefinitely, in the Dan L. Duncan Cancer Center Population Sciences Biorepository. Totally de-identified parts of participants' genetic information, and in some instances, clinical information, may be released to one or more scientific information sources. This may pose a privacy risk, as new techniques are developed that may allow scientists to trace information back to participants. Every reasonable effort will be made at all times to maintain the confidentiality of study records and of research information.

Section L: Cost/Payment

Delineate clinical procedures from research procedures. Will subject's insurance (or subject) be responsible for research related costs? If so state for which items subject's insurance (or subject) will be responsible (surgery, device, drugs, etc). If appropriate, discuss the availability of financial counseling.

No. All study-related costs associated with the EH Clinic visits and home visits will be covered by the research study.

If subjects will be paid (money, gift certificates, coupons, etc.) to participate in this research project, please note the total dollar amount (or dollar value amount) and distribution plan (one payment, pro-rated payment, paid upon completion, etc) of the payment.

Dollar Amount:

116

Distribution Plan:

Financial incentives include:

\$8 per clinic visit for travel costs (\$16 total) \$25 after participating in the baseline visit to the EH Clinic \$25 after participating in the phone call/survey at month 6 \$50 after exit visit at the EH Clinic at month 12

Travel costs as well as incentives related to the clinic visits will be paid at the time of the clinic visit. The \$25 after participating in the phone call/survey at month 6 will be made by cash or check from Baylor College of Medicine.

In addition, each participant in the interventional arm will receive a tailored set of tools to improve asthma control and home safety, with a value of up to \$350 per home. These tools may include, for example, dust mite-proof pillow encasements, a HEPA vacuum or air filter, integrated pest management services, and cleaning products. Control subjects who complete the study will be eligible to receive the intervention and related tools at the end of the study.

Section M: Genetics

How would you classify your genetic study?

DNA diagnostic study

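### The SAP's only stated attrition check has no arm qualifier, so it can miss arm-specific dropout that unbalances the completers behind the unadjusted exit comparison

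*SAP*

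**What the plan says.** The attrition check is a single sentence in the SAP, Statistical Analysis: "Baseline summary statistics were also compared between patients who completed the study (N=193) and those who did not (N=71". No arm is mentioned and no by-arm counts are given.

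The same paragraph describes the baseline summaries: "Summary statistics were calculated for the entire cohort, stratified by treatment group". The comparison of the arms at baseline is thus described for everyone enrolled, not for those who reached the exit visit.

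On the primary outcomes the SAP says: "The initial analysis of the outcome measures used an independent, two-sample, two-sided t-test, assuming equal variances". It compares exit values of ACT, MiniAQLQ and ED visits. Protocol Section G agrees: "Unadjusted analysis will be performed as the primary results". It then adds: "If baseline covariate imbalance is detected, the analysis will adjust for imbalanced covariates". That rule does not say in which population imbalance is to be sought, and the SAP's description of the primary analysis does not repeat it.

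Under Exploratory Analyses the SAP has repeated-measures models: "The LMM and GEE models include all available observations in the analyses and assume the data are missing at random". It also has regressions of the exit outcomes on candidate predictors, adjusted for study group and the baseline value.

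Protocol Section L describes what each arm receives. During the study, "each participant in the interventional arm will receive a tailored set of tools to improve asthma control and home safety", worth up to $350 per home. For the other arm, "Control subjects who complete the study will be eligible to receive the intervention and related tools at the end of the study".

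**The concern.** Comparing completers with non-completers over both arms shows whether those who stayed resemble those who left. That bears on generalisability. The validity of the treatment contrast depends on a different question: whether the completers in one arm resemble the completers in the other. If the people who leave differ between the arms, the pooled table can look balanced while the two analysed groups have drifted apart. Part of that drift then appears in the unadjusted exit difference as if it were a treatment effect.

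Dropout that differs by arm is plausible in this design. One arm receives tools during follow-up and up to five visits to the home, and Protocol Section H1 lists the home visits as an intrusion that some participants may mind. The other arm is followed by telephone between its clinic visits and is offered the intervention only on completion. With more than a quarter of enrollees not completing, the composition of the analysed groups matters.

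**Working it through.** **Inputs from the documents.** Completers 193 and non-completers 71 (SAP, Statistical Analysis). ACT standard deviation 4 and MCID 3, MiniAQLQ 0.6 and 0.5, ED visits 3 and 1.4, with 97 per group after 35% loss from 300 (SAP, Power and Sample Size).

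**The plan's own figures first.** 300 × 0.65 / 2 = 97.5, stated as 97. Power at 97 per group is 99.9% for ACT, 99.99% for MiniAQLQ and about 90% for ED visits. All agree with the SAP and are not in dispute. Attrition is 71 / (193 + 71) = 71/264 = 26.9%.

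**Assumptions not in the documents.** 132 per arm, completers are the participants with exit data, equal SDs at baseline and exit, and a baseline-exit correlation r of 0.5 to 0.7.

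**1. Dropout rates.** With 132 per arm, 42 versus 29 dropouts (31.8% vs 22.0%, Fisher p = 0.095) and 49 versus 22 (37.1% vs 16.7%, p < 0.001) both give the stated 193 and 71. The totals cannot show whether dropout differed by arm.

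**2. Opposite-direction dropout (extreme case).** Let f = 71/264 in each arm. If dropouts differ from completers by δ, the completers' mean sits at the arm mean minus fδ. Take δ = −g in one arm and +g in the other. The completers' means move by +fg and −fg, so the arms differ by 2fg. The expected pooled difference is (−g + g)/2 = 0. If dropout depends on the baseline score, the exit bias is 2fg × r.

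| g (ACT points) | Expected pooled difference | Baseline gap 2fg | Exit bias, r = 0.5 to 0.7 | Share of MCID 3 |
|---|---|---|---|---|
| 1 | 0 | 0.54 | 0.27-0.38 | 9-13% |
| 2 | 0 | 1.08 | 0.54-0.75 | 18-25% |
| 3 | 0 | 1.61 | 0.81-1.13 | 27-38% |

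**3. Selective dropout in one arm only.** The expected pooled difference is g/2. Its standard error is 4 × √(1/193 + 1/71) = 0.56. For g = 1, 2 and 3 the pooled test detects it about 15%, 44% and 77% of the time. The completers' baseline gap is fg = 0.27, 0.54 and 0.81.

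**4. Simulation of the extreme case.** 4,000 trials per setting, no treatment effect, ACT SD 4, and logistic dropout on baseline with opposite sign by arm. The slope was 0.5 or 0.75 per SD, giving mean baseline gaps of about 1.0 and 1.5 points. Each cell shows the proportion of trials with p < 0.05.

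| Test | Slope 0.5 | Slope 0.75 |
|---|---|---|
| Pooled completer check | 4.6-5.3% | 5.0-5.5% |
| Completers' baselines, arm versus arm | 43-44% | 76% |
| Completion-by-arm interaction on baseline | 93-94% | nearly 100% |
| Unadjusted exit t-test (type I error) | 14-25% | 24-44% |
| Exit comparison adjusted for baseline (type I error) | 4.6-5.0% | 4.9-5.1% |

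Without selective dropout every test stays near 5%.

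**The case against.** The best reply is that the SAP already contains analyses that use baseline. The mixed model and GEE take in all available observations with a group-by-time term, and the predictor regressions adjust for group and baseline score, which makes them close to an ANCOVA. In the simulation a baseline-adjusted comparison held its error rate. This stands as partial mitigation. However, these analyses are labelled exploratory, the regressions are aimed at predictors rather than the treatment effect, and none of them shows who left which arm. A reader might infer that the plan leaves attrition wholly unaddressed; these analyses contradict that.

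Three further stronger readings are tempting and not supported:

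- *That the pooled check is blind.* Exact cancellation needs equal dropout with equal and opposite gaps. With one-sided selection the check has partial power (step 3).
- *That the full baseline gap reaches the result.* Dividing 1.61 by 3 suggests 54% of the MCID, but the outcome is measured at exit, so the gap has to be scaled by the baseline-exit correlation.
- *That the incentives predict the opposite-direction pattern.* They bear on how many leave each arm. Nothing in the Protocol implies that sicker controls and healthier home-visit participants leave. The cash payments ($116 in total, including $50 at exit) do not differ by arm.

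It is also fair to say that pooling is inferred. The sentence does not say that arm was ignored, and its paragraph opens with summaries by treatment group. The pooled reading is still the likelier one, given two totals and no qualifier.

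**Conclusion.** The point holds as a gap in the diagnostics for the primary comparison. As written, the stated check cannot establish that the analysed arms remain comparable, and a by-arm check would do so far better with data already held. A reader might infer that dropout did bias this trial. The documents do not support that, because they give no dropout by arm.

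The size is conditional. In the extreme case of step 2 the exit bias is about 0.3 to 1.1 ACT points, or 9% to 38% of the MCID, for gaps of 1 to 3 points. With selection in one arm only it is half that, and the pooled check would sometimes catch it. These figures rest on the assumed equal split, gaps and correlation. The protection from baseline adjustment seen in step 4 holds because dropout there depends only on the baseline score; dropout driven by unrecorded changes during follow-up would not be corrected.

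**What to change.** Add the following, labelled post hoc, since the SAP revision of 9/9/2018 is written in the past tense and already reports the completion totals:

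1. Number, timing and reason for non-completion, by arm.
2. Baseline characteristics by arm and completion status, four columns in all.
3. A model of completion on baseline ACT, MiniAQLQ, ED visits, age and sex, with arm interactions.
4. Beside each primary exit comparison, a sensitivity analysis adjusted for the baseline value of that outcome and the stratification factors (age group and sex in the SAP's Randomization section), whatever any imbalance test shows.

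Item 4 should not be triggered by a significance test among completers. In step 4 that test flagged only 43-44% of trials at the smaller slope, so a test-then-adjust rule would often leave the bias in place. Keep the existing pooled table, and describe it as evidence on generalisability only.

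The cost is two tables and a few models on data already held. The downside is a little more reporting and a result that may look less reassuring.

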The study will use simple paired methods (e.g., Wilcoxon signed-rank test) to compare changes in primary outcome measure (health care utilization) from the pre- to post-intervention period. Longitudinal analysis (e.g., generalized estimating equation or mixed-effects linear regression model) techniques will be used to examine changes in health care utilization over time with an indicator for time periods, controlling for potential confounders, such as gender, income, education, asthma severity, exposure to cigarette smoke and race/ethnicity. Subgroup analyses will be performed in pre-specified groups. P-values less than 0.05 (2-sided) will be considered statistically significant. Analyses will be carried out using the current versions of SAS, Stata or R. Geospatial models of selected risk and distribution parameters will also be developed and assessed for spatial patterns.

Section H: Potential Risks/Discomforts

H1. Potential Risks/Discomforts

Describe and assess any potential risks/discomforts; (physical, psychological, social, legal, or other) and assess the likelihood and seriousness of such risks:

INTERVIEWS/QUESTIONNAIRES The questionnaires contain a few questions that some participants may feel are too personal or sensitive in nature. Participants can refuse to answer any question that makes them feel uncomfortable. Efforts will be made to ensure that participants understand that such refusal is their right and that the investigators understand and appreciate their candor.

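### The primary exit comparison uses neither baseline values nor randomisation strata: it is valid, but its mean differences could be estimated more precisely at no data cost

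*SAP*

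**What the plan says.** SAP, Statistical Analysis (Primary Outcome Analyses): "The initial analysis of the outcome measures used an independent, two-sample, two-sided t-test, assuming equal variances". The alternatives are Welch's test, nonparametric methods or a transformation. ED visits are also compared by Wilcoxon rank-sum and, as any visit or none, by Fisher's exact test. For the effect measures, "we calculated the raw mean difference (MD) for the continuous variables" ACT and MiniAQLQ, and "the odds ratio (OR) for the binary variable, ED visits". None of these uses baseline values or strata.

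Protocol Section G (data analysis) makes the choice explicit: "Unadjusted analysis will be performed as the primary results". It adds a conditional step, "If baseline covariate imbalance is detected, the analysis will adjust for imbalanced covariates", which the SAP does not repeat.

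The information for an adjusted comparison exists. The SAP (Exploratory Analyses) says that all three primary outcomes were recorded at baseline. The SAP (Randomization) gives age and sex as strata; Protocol F1 gives age only.

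Other planned analyses touch on baseline:

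- The exploratory mixed model and GEE treat baseline as one of the repeated outcomes: "we included time, study group, and the interaction between time and study group". No strata are listed.
- The exploratory predictor regressions include study group and the baseline value, with ED visits as yes/no.
- Post hoc models examine age-by-group and gender-by-group interactions.
- Protocol Section G plans a longitudinal utilisation model "to examine changes in health care utilization over time with an indicator for time periods, controlling for potential confounders". Gender is among its examples.

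**The concern.** A patient's exit score usually depends in part on the score at entry. A comparison of exit means that ignores the entry score leaves this predictable variation in the error term, so the interval for the treatment effect is wider than the data require. Stratified randomisation also balances the groups on the strata, and an analysis without them does not credit that balance in its standard error.

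At stake is the width of the intervals for the differences in mean ACT, MiniAQLQ and number of ED visits. The question is whether the loss is large enough to mention, and whether another planned analysis already recovers it.

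**Working it through.** **Inputs.** From the SAP, Power and Sample Size: n = 97 per group, two-sided 0.05; SD 4 and difference 3 (ACT); SD 0.6 and difference 0.5 (MiniAQLQ); SD 3 and difference 1.4 (ED visits). From the SAP, Statistical Analysis: 193 completers and 71 non-completers, 264 in all. Not in the documents: the within-group baseline-exit correlation r, assumed to be 0.3, 0.5 or 0.6. Eligibility requires poorly controlled asthma (Protocol F1), which narrows the baseline range and may favour the low end.

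**Step 1: the plan's own figures.** SE = SD × √(2/97), that is 0.574, 0.0862 and 0.431. By the noncentral t with 192 df, power is 99.94% (ACT), 99.99% (MiniAQLQ) and 89.9% (ED visits). These match the stated figures, including about 90% "power to detect a difference of 1.4 in annual ED visits between the two groups".

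**Step 2: adjust for baseline.** Residual SD = SD × √(1 − r²), so the variance is multiplied by 1 − r² = 0.91, 0.75 or 0.64. Residual df = 194 − 6 = 188 (intercept, group, baseline, three terms for four age-by-sex strata). The 95% half-width is t × SE, with t ≈ 1.97.

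| | t-test | r = 0.3 | r = 0.5 | r = 0.6 |
|---|---|---|---|---|
| ACT half-width | 1.13 | 1.08 | 0.98 | 0.91 |
| MiniAQLQ half-width | 0.170 | 0.162 | 0.147 | 0.136 |
| Mean ED visits half-width | 0.85 | 0.81 | 0.74 | 0.68 |
| Power, 1.4 ED visits | 89.9% | 92.4% | 96.2% | 98.1% |

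The ED power row is a linear-model approximation.

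**Step 3: strata.** In simulation with 264 randomised in four strata and random loss to 193, the type I error of the t-test was 0.051, 0.044 and 0.032 when the strata explain 5%, 10% and 20% of outcome variance (assumed). Ignoring them makes the test at most conservative.

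**Step 4: does the mixed model recover the loss?** With f = 193/264 = 0.731, equal variances, loss at random and the 6-month value ignored, variance relative to the t-test is:

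| Contrast | Formula | r = 0.3 | r = 0.5 | r = 0.6 |
|---|---|---|---|---|
| Mixed model, exit | 1 − r²(1 − f) | 0.98 | 0.93 | 0.90 |
| Mixed model, baseline to exit | (1 − r²) + (1 − r)²f | 1.27 | 0.93 | 0.76 |
| Exit regressed on baseline | 1 − r² | 0.91 | 0.75 | 0.64 |

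With the 6-month value (assumed 105 to 125 per group, and a 6-month-to-exit correlation up to r + 0.2), the exit contrast falls no lower than 0.93, 0.87 and 0.83. The mixed model recovers part of the gain.

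**Step 5: the other analyses.** The predictor regressions come close, since they contain group and baseline. But they are exploratory, aim at predictors, select further covariates largely from the data, and model ED visits only as yes/no. The interaction models bring in age and gender, but post hoc and as tests of heterogeneity. The Protocol's utilisation model, as written, names a time indicator but no study-group term, and the SAP does not carry it forward as primary. The Protocol's imbalance rule chooses covariates by observed imbalance, not by prognostic value. None is a fixed treatment comparison with baseline and strata.

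**Step 6: ED visits under the tests actually planned.** With negative binomial counts (assumed means 3 and 1.6, SD 3 in each group), simulated power is about 0.89 for the t-test but above 0.99 for Wilcoxon and Fisher. The adjusted regression with robust standard errors reached 0.910, 0.946 and 0.972 at realised r of 0.29, 0.50 and 0.62. With a common dispersion and pooled SD 3, the order reverses: about 0.92 for the t-test and 0.83 for Wilcoxon. With control mean 2 and realised r of 0.23, adjustment added nothing (0.868 to 0.869).

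**The case against.** The strongest reply is that this is a declared design choice. The Protocol makes the unadjusted result primary, the t-test is valid, and at r = 0.3 the ACT half-width moves by only 0.05 points against an MCID of 3. Every gain rests on a correlation that the documents do not give. All of this stands, and it is why the point is minor.

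A second reply is that the exploratory section already fits the exit value on group and baseline. This largely stands for ACT and MiniAQLQ: the gap is a fixed covariate set with strata and a stated treatment contrast. For the number of ED visits the gap is wider, since that regression uses yes/no only. The absence of age from the Protocol's utilisation model should not be pressed, because its covariate list is given as examples.

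A third reply concerns ED power. A reader might infer from the rise from 89.9% to as much as 98.1% that the plan is short of power for ED visits. The documents do not support that. The rise applies to the t-test on the mean, while the plan also uses Wilcoxon and Fisher tests, whose power depends on the count distribution and can exceed that of the adjusted comparison. This objection stands in full.

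**Conclusion.** The point holds as a loss of precision in the three mean differences. The variance reduction forgone is 9%, 25% or 36% at r = 0.3, 0.5 or 0.6, with half-widths as in the first table. For ACT and MiniAQLQ the benefit is interval width only. For ED visits the t-test on the mean difference would gain power, but this is not an established gain for the plan as a whole.

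A reader might infer that the unadjusted comparison is biased or invalid. It is not: randomisation supports it, and ignoring the strata errs at most on the conservative side. Missing exit data are a separate matter. Nor does the point extend to the ED odds ratio: an adjusted odds ratio is a different effect measure, and adjustment tends to widen its interval on the log scale.

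The sizes rest on the assumed r, the SAP's SDs and 97 per group. Label: free improvement; severity: consider.

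**What to change.** Keep the unadjusted results as primary, and leave the Protocol's imbalance rule in place as protocol-specified. Beside them add one fixed adjusted comparison per primary outcome:

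- **ACT and MiniAQLQ:** linear regression of the exit score on study group, baseline score and the strata actually used.
- **ED visits:** linear regression of the exit visit count on study group, baseline visits and the same strata, with robust (HC3) standard errors. This keeps the difference in mean visits on which the sample size was based.

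First reconcile the strata: age only in Protocol F1, age and sex in the SAP (Randomization). If an adjusted odds ratio is also given, state that it is a different effect measure from the unadjusted one. Keep the mixed model and GEE as exploratory.

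The cost is one extra analysis per outcome and no new data. The SAP revision of 9/9/2018 is written in the past tense and gives completer counts. The addition must therefore be dated, labelled as specified after data collection, and reported whatever it shows. It cannot claim prespecified status.
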